7.2. Overall Study Design

The study events schedule is shown in [Table 3](#). This is a double-blinded, randomized, placebo-controlled, in-clinic, Phase 1, single-dose, IM, sequential dose-escalation study in healthy adults aged 18-55. Healthy volunteers will be assigned to 1 of 5 cohorts of Scopolamine HBT dosage groups: 0.005, 0.007, 0.011, 0.014, or 0.021 mg/kg, or receive the placebo, administered by IM injection to the anterior thigh. In each cohort, 6 to 9 subjects will receive active drug and 2 to 3 subjects will receive placebo. Each cohort will have at least 3 male and 3 female subjects enrolled among the first 8 subjects in the dosing group to ensure that at least 1 male subject and 1 female subject in each dosing group receive active drug. If nonextreme DLTs are observed in any of the cohorts, 4 additional subjects, 3 active and 1 placebo, may be added to each cohort.

On the first day of dosing for each cohort, 2 subjects will be dosed (1 active and 1 placebo). Upon review of AE data for both subjects at 24 hours post dose (± 1 hour), the PI and the medical monitor will determine if it is safe to proceed with dosing the remaining 6 of the first 8 subjects.

New subjects will not be enrolled into the next higher dosage group until at least 8 subjects in the previous cohort have completed the Day 8 follow-up visit without the occurrence of DLTs, predefined as requiring termination of the study; the Data Safety Monitoring Board (DSMB) has reviewed data and made a dose-escalation recommendation to the sponsor; and the sponsor concurs with the DSMB recommendation. The sponsor must approve dose escalation. Dose escalation cannot occur until after sponsor approval of the DSMB recommendation and notification of the investigator(s), not at the time of the DSMB recommendation. [Table 4](#) shows study events for pre dose through 36 hours post dose.

This Phase 1, GCP-compliant study is being performed to collect reliable PK data for Scopolamine HBT administered IM, as these are not found in the published literature, and to inform future studies. The goal of this study is to assess safety, tolerability, and PK, including the assessment of dose exposure proportionality, of Scopolamine HBT in the 5 cohorts.

Table 3: Study Events Schedule

Study Phase	Screening	Baseline ^a	Treatment ^a			Follow-up ^b			
Procedures	Study Day	-30 to -2	-1	1 ^c	2 (24 ± 1 h)	3 (48 ± 1 h)	4 (+ 2 days)	8 (+2 days)	30 (+ 7 days)
Informed Consent		X							

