7.6. Dose-adjustment Criteria

New subjects will not be enrolled into the next higher dosage group until at least 8 subjects in the previous cohort have completed the Day 8 follow-up visit without the occurrence of DLTs, and the DSMB has made a recommendation to the sponsor regarding dose escalation. The sponsor must approve the dose escalation and notify the investigator(s) before any new subjects can be enrolled. The occurrence of any DLT(s) would result in the immediate discontinuation of dosing and study enrollment, pending a review of study data by the PI, research monitor, PVG physician, the DSMB, and the sponsor.

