7.6.1. Safety Criteria for Dose Adjustment or Stopping Doses

For the purposes of determining continued dosing within a cohort or dose escalation to a subsequent planned cohort, stopping rules are based on the emergence of DLTs. Nonextreme and extreme DLTs will be considered related AEs/serious adverse events (SAEs) and will be recorded/reported as such.

Dosing of study drug and study enrollment will be halted (temporarily or permanently) as follows:

- Occurrence of any extreme DLT (dosing and enrollment to be halted immediately; PI, research monitor, PVG physician, and DSMB will review and make a recommendation to the sponsor, which will determine if dosing and enrollment may continue);
- Emergence of a specified number (see [Table 6](#)) of nonextreme DLTs among subjects in a particular dosage group (DSMB will review to determine whether dosing and enrollment may continue);
- Occurrence of an SAE not already designated as an extreme or nonextreme DLT, determined to be possibly, probably, or definitely related to the investigational product; dosing and enrollment to be halted immediately until the DSMB has completed a safety review; and

- Sponsor, DSMB, or PI's clinical judgment warrants stopping based on ongoing review of the safety profile.

The maximum tolerated dose will be the highest dose at which none of the following has been observed:

- An extreme DLT in any one subject;
- A nonextreme DLT in 2 of the first 4 subjects or in 3 subjects at any time; and
- Any SAE, not already categorized as a DLT that is considered to be possibly related, probably related, or definitely related to the study drug.

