7.6.1.2. Nonextreme Dose-Limiting Toxicities

Nonextreme DLTs are AEs that do not meet the criteria for extreme DLTs but are serious conditions that require immediate medical attention and monitoring. The incidence and severity of these events will be used to determine whether (1) the total cohort size will be increased from 8 to 12 and (2) the need to suspend dosing until the DSMB has completed a safety review and made a recommendation to the sponsor ([Table 6](#)). Nonextreme DLTs include:

- Respiratory
 - Spontaneous respiratory rate < 8 or > 25 breaths per minute, with oxygen saturation less than 90%, which cannot be explained by agitation or other behavioral symptoms and that does not respond immediately to oxygen supplementation via nasal cannula or face mask but for which there is recovery without sequelae prior to the need for intubation
 - Dyspnea at rest
 - Symptomatic bronchospasm
- Neuropsychiatric
 - Neuropsychiatric symptoms (eg, delirium, paranoia, and/or hallucinations) requiring treatment with physostigmine or other medication(s) and, in the opinion of the investigator, responded adequately to treatment
 - Persistent neuropsychiatric symptoms, defined as a score of 4 or higher on any one item or a total score of 40 or higher on the BPRS assessment at the 48-hour, post-dose evaluation
 - Paresthesia that interferes with any activity
 - Athetoid movement
- Cardiac
 - Hypertension, which cannot be explained by agitation or other behavioral symptoms, requiring antihypertensive medication
 - Cardiac arrhythmias or changes that are deemed clinically significant but do not cause the subject to be hemodynamically unstable
 - QTc is > 450 msec for males or > 470 msec for females and has increased > 60 msec from baseline
 - Supraventricular tachycardia alone without hemodynamic compromise
 - Bigeminy or trigeminy not associated with hypotension
- Renal
 - Increase of serum creatinine by ≥ 0.3 mg/dL (≥ 26.4 μ mol/L) or increase to $\geq 150\%$ from baseline or urine output < 0.5 mL/kg/hour for > 6 hours
- Injection Site Reaction

- Any reaction determined to be severe, as defined by the FDA's guidance for injection site reactions ([Appendix B](#)).

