7.6.1.3. Serious Adverse Events

In the event of an SAE that has not already been designated as a DLT but has been determined by the PI, research monitor, and PVG physician to be possibly, probably, or definitely related to the study drug, the PI is to discontinue dosing study drug and study enrollment immediately until the DSMB has completed a safety review and made a recommendation to the sponsor. The sponsor must concur with the recommendation and notify the investigator(s) before enrollment can be resumed (see Section [11.2.2](#) for SAE criteria.)

Table 6: Progression of Dosing Related to Dose-Limiting Toxicity Events

Dose-Limiting Toxicity	Number of Subjects	Action	Follow-up
Extreme DLT	1	Dosing and enrollment halted	PI, research monitor, PVG physician, and DSMB review; sponsor determines whether trial should continue
Nonextreme DLT	1 of first 4 in a cohort (or 2 in the first 8)	Dosing halted	PI, research monitor, PVG physician, and DSMB review; sponsor determines whether to increase cohort size from 8 to 12
	2 of the first 4 in a cohort (or 3 total)	Dosing and enrollment halted	PI, research monitor, PVG physician, and DSMB review; sponsor determines whether trial should continue
SAE Not Already Designated as a DLT (except unrelated)	1	Dosing and enrollment halted	DSMB to make recommendation to sponsor whether trial should continue

In summary, if any one subject has an extreme DLT, enrollment and dosing will be halted pending review by the PI, research monitor, PVG physician, and DSMB. In making its determination, the DSMB will review all relevant data and obtain additional input as needed. As a guideline to the DSMB, it is suggested that if a nonextreme DLT is observed that the DSMB consider an increase in the cohort sample size from 8 to 12 if one nonextreme DLT is observed in the first 4 subjects or 1 or 2 nonextreme DLTs are observed in the first 8 subjects and that enrollment be halted if nonextreme DLTs are observed in 2 of the first 4 subjects in a cohort or in a total of 3 subjects at any time.

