9. TREATMENT OF SUBJECTS

9.1. Dose Administration and Follow-up Periods/Study Visits

9.1.1. Treatment

Subjects will be assigned to 1 of 5 cohorts/dosage groups (Scopolamine HBT: 0.005, 0.007, 0.011, 0.014, or 0.021 mg/kg or placebo). The investigational product will be administered by

IM injection to the anterior thigh. In each cohort, 6 to 9 subjects will receive active drug and 2 to 3 subjects will receive placebo. Each cohort will have at least 3 male and 3 female subjects enrolled among the first 8 subjects in the dosing group to ensure that at least 1 male subject and 1 female subject in each dosing group receive active drug. If nonextreme DLTs are observed in any of the cohorts, 4 additional subjects, 3 active and 1 placebo, may be added to each cohort.

On the first day of dosing for each cohort, 2 subjects will be dosed (1 active and 1 placebo). Upon review of the AE data for both subjects at 24 hours post dose (\pm 1 hour), the PI and the medical monitor will determine if it is safe to proceed with dosing the remaining 6 of the first 8 subjects.

New subjects will not be enrolled into the next higher dosage group until at least 8 subjects in the previous cohort have completed the study Day 8 follow-up visit without the occurrence of DLTs, predefined as requiring termination of the study; the DSMB has made a recommendation to the sponsor; and the sponsor concurs with the DSMB recommendation regarding dose escalation following a review of study data. The sponsor must approve dose escalation. Dose escalation cannot occur until after sponsor approval of DSMB recommendations and notification of the investigator(s), not at the time of the DSMB recommendation.

All subjects participating in the study will be monitored closely throughout the in-clinic phase of the study. Staff will be available with the appropriate expertise to assess and manage neuropsychiatric problems that may arise. The PI and/or physician designee will be in the treatment room during dosing and for 4 hours post dose. A psychiatrist will be available by phone to consult with the investigator throughout the study. At the investigator's request, the psychiatrist will come to the clinic to evaluate a subject. A crash cart, which will include specific drugs to treat Scopolamine HBT effects (eg, physostigmine and diazepam), will be in the immediate area where subjects are residents.

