9.1.1.2. Study Day -1 (One Day Prior to Dosing)

If subjects qualify, they will be asked to return to the clinic on the day prior to dosing to check in for the in-clinic stay. Subjects will be given standardized meals during their in-clinic stay. Subjects with dietary restrictions will receive the appropriate food substitutes to ensure proper nutrition and to prevent potential biological material from interfering with the PK evaluation of the blood samples.

All eligible subjects are considered alternates until they are dosed. Eligible subjects not dosed on Day 1 will be considered for the next dosing day. Subjects who are administered the study drug will remain at the study site for 48 hours after dosing (until the morning of Day 3).

On the day prior to dosing (ie, Day -1), the following will be performed:

- Physical examination of all major systems including general appearance, EENT, chest/respiratory, heart/cardiovascular, abdomen/gastrointestinal, lymph nodes/spleen, genitourinary, musculoskeletal, skin, neurological, and hepatic
- Medical history update: AEs identified/reported prior to dosing will be added to the medical history
- 12-lead ECG after the subject has been supine for at least 5 minutes
- Vital signs (including systolic and diastolic blood pressure, heart rate, respiration rate, body temperature, and pulse oximetry) collected after the subject has been resting in a supine position for at least 5 minutes
- Weight measurement and BMI confirmation; Day -1 weight will be used for dose determination on Day 1

- Clinical laboratory tests to include hematology and coagulation (Section 11.1.9.1) and serum chemistry (Section 11.1.9.2)
- Urinalysis (Section 11.1.9.3)
- Serum pregnancy test (Section 11.1.9.4) for all females regardless of childbearing potential
- Urine drug screen (Section 11.1.9.5)
- Alcohol breathalyzer test
- SCID-5-CT (customized) will be administered by a psychologist to determine whether there is evidence of major DSM-5 Axis I or II disorder

Note: Subjects who are designated alternates and readmitted on another day will not have the SCID repeated (see Section 11.1.6).

- BPRS will be administered by a psychologist or trained clinician
- C-SSRS (Since Last Visit version) and DSST will be administered by study staff
- Prior/concomitant medications/treatments
- Review of inclusion/exclusion criteria

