11. SAFETY ASSESSMENT

Safety monitoring will be conducted throughout the study; therefore, safety concerns will be identified by continuous review of data by the PI, clinic staff, clinical trial monitor, research monitor, and [REDACTED].

Study Safety Management: The PI, research monitor, [REDACTED] PVG physician, and IRB will review any safety concern.

An independent DSMB is required for this study. The DSMB will be convened to review safety data and provide recommendations to the sponsor's representative. Prior to any data being provided to the DSMB, it must be reviewed and approved for release by a study biostatistician in collaboration with the [REDACTED] biostatistician. The DSMB will review cumulative study data during scheduled in-process and ad hoc reviews to evaluate safety, study conduct, and the scientific validity and integrity of the trial. After each review of study data, the DSMB will make a recommendation to the sponsor's representative. DSMB recommendations will be documented and provided in writing (via the DSMB Chair Recommendation Form) to the [REDACTED] [REDACTED]. The sponsor's representative will then decide whether to continue, modify, or suspend the study. The [REDACTED] will communicate the final decision to the investigator, who in turn will notify the IRB as appropriate. The [REDACTED] regulatory affairs scientist will communicate the final decision to the FDA, as appropriate. A description of the DSMB's roles and responsibilities, functions, reporting requirements, meeting frequency, and the study stopping/continuation criteria is included in the DSMB charter.

Research Monitor: The DoD research monitor is responsible for overseeing the safety of the research and reporting observations/findings to the IRB or a designated institutional official. The research monitor will review all unanticipated problems involving risks to subjects or others associated with the protocol and provide an independent report of the event to the IRB. The research monitor may discuss the research protocol with the investigators; shall have authority to stop a research protocol in progress, remove individual human subjects from a research protocol, and take whatever steps are necessary to protect the safety and well-being of human subjects until the IRB can assess the research monitor's report; and shall have the responsibility to promptly report his or her observations and findings to the IRB or other designated official and the [REDACTED].

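### The first-4 nonextreme-DLT trigger has no matching observation point: after the sentinel pair, all six remaining subjects may be dosed with no stated interval

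*Protocol*

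**What the plan says.** **The trigger.** Table 6 (Protocol 7.6.1.3) halts dosing on a nonextreme DLT in "1 of first 4 in a cohort (or 2 in the first 8"). The follow-up is a review of whether to enlarge the cohort from 8 to 12. At 2 of the first 4, or 3 in total, dosing and enrollment both halt and the sponsor decides whether the trial continues. The maximum-tolerated-dose definition in Protocol 7.6.1 lists "A nonextreme DLT in 2 of the first 4 subjects or in 3 subjects at any time" among the disqualifying events. SAP 3.3.1 and 6.4 repeat the first-4 counts.

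**The scheduled checkpoint.** Two subjects, one active and one placebo, are dosed on the first day of each cohort. After a 24-hour adverse event review, "the PI and the medical monitor will determine if it is safe to proceed with dosing the remaining 6 of the first 8 subjects" (Protocol 7.2; likewise the synopsis, 5.4, 9.1.1 and the Medical Monitor paragraph of section 11). No later hold, minimum interval or daily limit is stated.

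**The event-driven halt.** Protocol 7.6 adds: "The occurrence of any DLT(s) would result in the immediate discontinuation of dosing and study enrollment", pending review.

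**Supervision.** Under Protocol 9.1.1 a physician "will be in the treatment room during dosing and for 4 hours post dose", and cardiovascular monitoring is continuous for 24 hours.

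**SAP 6.4** reasons from the halt rule that no more than one extreme DLT can occur in a cohort before stopping.

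**The concern.** A stricter threshold for the first four subjects can limit exposure only if subjects 3 and 4 are observed before subjects 5-8 are dosed. Nothing in the two documents provides for that. The single scheduled review has seen one active subject and then opens dosing for all six others.

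The immediate halt in 7.6 can stop only doses not yet given, and some nonextreme DLTs show late. One criterion is "a total score of 40 or higher on the BPRS assessment at the 48-hour, post-dose evaluation" (Protocol 7.6.1.2). The renal criterion needs more than 6 hours of low urine output, or a creatinine result from the 24- or 48-hour laboratory tests. The first post-dose BPRS is at 6 to 8 hours.

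At stake is avoidable exposure of 3 or 4 healthy volunteers per cohort, who gain nothing from the dose. A second consequence is that SAP 6.4 presents as a property of the design something that holds only if each subject's outcome is known before the next is dosed.

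**Working it through.** **Inputs.** Subjects 1-2 include 1 active (Protocol 7.2). Subjects 3-8 form a block of 5 active and 1 placebo (SAP 3.6). The documents give no expected DLT rate, so p (any DLT, per active subject) and q (extreme DLT, per active subject) are assumptions shown as ranges. DLTs are taken as independent and absent on placebo. The value 23.5% is the detection threshold in SAP 3.5, not an expected rate.

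**The plan's own figures reproduce.** SAP 3.5: 1 - (1 - 0.235)^6 = 0.7996, the stated 80%. SAP 6.4: the Clopper-Pearson 80% upper bounds are 0.32 for 0 of 6 and 0.51 for 1 of 6, as printed.

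**Who is exposed.** The one placebo among subjects 3-8 falls on subject 3 or 4 with probability 2/6. So subjects 3-4 hold 2 active with probability 2/3 (leaving 3 active in 5-8) or 1 active with probability 1/3 (leaving 4).

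**How often the gap could matter.**
- A: sentinel clear and at least one DLT in subjects 3-4: (1 - p) × [2/3 × (1 - (1 - p)^2) + 1/3 × p].
- B: sentinel clear and DLTs in both, the first-4 count at which continuation of the trial is questioned: (1 - p) × 2/3 × p^2.

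| Assumed p | A | B |
|---|---|---|
| 2% | 3.2% | 0.03% |
| 5% | 7.8% | 0.16% |
| 10% | 14.4% | 0.6% |
| 23.5% | 27.1% | 2.8% |

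For example, at p = 10%, A = 0.9 × (2/3 × 0.19 + 1/3 × 0.10) = 0.9 × 0.16 = 0.144. Given A, subjects 5-8 hold on average 3.2 active. A is an upper limit, because it counts acute DLTs that ordinary spacing would catch in time.

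**SAP 6.4.** Let T(n) = 1 - (1 - q)^n - n × q × (1 - q)^(n-1), the chance of two or more events among n active. If subjects 3-8 are all dosed before any event shows, two or more extreme DLTs after a clear sentinel have probability (1 - q) × T(5). If they are dosed as 2 and then 4, each group together, it is (1 - q) × {2/3 × [q^2 + (1 - q)^2 × T(3)] + 1/3 × (1 - q) × T(4)}.

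| Assumed q | 3-8 together | 3-4, then 5-8 |
|---|---|---|
| 1% | 0.1% | 0.05% |
| 2% | 0.4% | 0.2% |
| 5% | 2.1% | 1.0% |
| 10% | 7.3% | 3.4% |

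The probability is small and a hold roughly halves it, but it is not zero under either schedule. Upper bounds for two events (90th percentile of a beta distribution): 2 of 6, beta(3, 4), 0.667; 2 of 9, beta(3, 7), 0.490.

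**The case against.** The strongest reply is that the harm needs a premise the documents do not state. A reader might infer that subjects 3-8 are dosed together; no text says so. Protocol 9.1.1.2 points to several dosing days: "Eligible subjects not dosed on Day 1 will be considered for the next dosing day". The tight early blood-sampling windows and repeated ECGs also make literal simultaneous dosing unlikely. This stands, though neither provision guarantees hours of spacing.

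A reader might also infer that subjects 5-8 have no protection, or that up to 27% of cohorts would be harmed. Neither follows. Protocol 7.6 halts on any DLT, which is stricter than Table 6, and supervision is close. One nonextreme DLT in the first 4 leads to review of cohort expansion rather than to stopping, so subjects 5-8 might be dosed at that level anyway, after review. The protocol also offers the nonextreme counts as guidance to the DSMB, and a count rule can work without a scheduled hold. These points limit the size. They do not supply the missing observation: without spacing, the review would come after the doses it is meant to inform.

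Third, section 11 says that a description of "the study stopping/continuation criteria is included in the DSMB charter". That document was not available and may already set spacing. Finally, a full second review is more than acute DLTs need, and a 24-hour check would miss the 48-hour BPRS criterion, as the sentinel review already does. Both points are fair and shape the remedy.

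**Conclusion.** The concern holds in conditional form. A trigger based on the first four subjects has no matching observation point, and the plan permits, without stating, dosing close enough to defeat it. Probability A (3% to 27%) is an upper limit at assumed DLT rates; probability B is 0.03% to 2.8%. Both assume independent events and none on placebo. Priority is low to moderate.

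Separately, the SAP 6.4 statement is not guaranteed by the halt rule, because several subjects can be dosed before an event appears. A reader might infer that the DLT risk estimates are therefore invalid. They are not: the final Clopper-Pearson analysis uses observed counts and is unaffected. Only the explanatory sentence and the range of Table 8 need correction.

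**What to change.** **Protocol 7.2 and 9.1.1, with matching text in the synopsis, 5.4 and the Medical Monitor paragraph of section 11.** State that subjects 5-8 are not dosed until subjects 3 and 4 have been observed for a stated minimum period. One way is to dose subjects 5-8 on a later day, after the PI and medical monitor have checked the adverse events of subjects 3-4 at 24 hours. A 48-hour hold would be needed to cover the BPRS criterion and the second creatinine. If the DSMB charter already sets spacing, state that in the protocol instead. The sentinel review, Table 6 counts, maximum-tolerated-dose definition and randomization blocks can stay as they are.

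**SAP 6.4.** Say that more than one extreme DLT can occur before a halt when several subjects are dosed before an event appears. Extend the extreme-DLT row of Table 8 to 2 events: 0.67 for 2 of 6 (already printed in the row for two nonextreme DLTs in the first 8) and 0.49 for 2 of 9.

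**Cost.** One extra dosing day per remaining cohort, with its physician cover and any repeat Day -1 assessments for readmitted alternates, and about 2 to 5 calendar days. If the first dose is on calendar day 0 and subjects 5-8 are dosed on day 4 to 7, their Day 8 visits (Study Days 8-10, that is 7 to 9 days after dosing) fall on days 4 + 7 = 11 to 7 + 9 = 16. That is well inside the six-week (42-day) minimum before escalation in SAP 3.1.
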